## 1. Background

For several decades now, hematopoietic stem cell transplantation (HSCT) has been the main curative treatment modality for patients with various primary immunodeficiency (PID) syndromes (1). Because only a small proportion of patients with inherited diseases have an HLA-identical related donor, transplantation of stem cells from a matched unrelated donor (MUD) or a haploidentical mismatched related donor (MMRD) is a widely used variant of HSCT. The most serious complications of HSCT from an alternative donor are acute and chronic graft-versus-host disease (GVHD) and graft failure for haploidentical donor HSCT (especially for non-SCID PID), which often leads to prolonged morbidity and late immune reconstitution with secondary immunodeficiency. Despite the fact that the frequency of acute GVHD after alternative donor HSCT does not exceed 20%, the incidence rate of life-threatening acute GVHD (higher than grade II) is more than 10% (2), (3). The use of immunomagnetic technology for T cell depletion or positive CD34 selection is a routine method of GVHD prevention after haploidentical HSCT. However, this method leads to prolonged immunoincompetence in patients, resulting in a high incidence of infections and associated complications, which affect the outcome of HSCT (4).

TCR alpha/beta depletion coupled with CD19 graft depletion is a promising technology, potentially capable of reducing the incidence of acute and chronic GVHD and enhancing immune reconstitution (5). T cells with alpha/beta -chain TCRs are the major inducers of GVHD, and their elimination from the graft can decrease the frequency of this complication (6). At the same time, T cells with gamma/delta-chain TCRs combine conventional adaptive features with rapid innate-like responses that place them in the initiation phase of immunoreactions (7). These cells are able to recognize target cells through MHC-independent mechanisms involving activating receptors (eg, gamma/delta TCR, NKG2D, TLRs, and DNAM-1), resulting in the rapid production of cytokines (IFN- $\gamma$  and tumor necrosis factor- $\alpha$ ) and a cytotoxic response. Because their immunologic response does not depend on MHC, gamma/delta T cells, in contrast to alpha/beta T cells, play a limited role in the development of GVHD, the pathogenesis of which is based on HLA alloreactivity. Conversely, gamma/delta T cells have high activity against intra- and extracellular pathogens (8), (9).

## **2. Study Design**

### **2.1 Study Type**

Interventional, Phase II/III, open-label

### **2.2 Primary Purpose**

To evaluate safety and efficacy of allogeneic hematopoietic stem cell transplantation from unrelated and haploidentical donors TCR alpha beta graft depletion in pediatric patients with primary immunodeficiencies.

### **2.3 Secondary purposes**

- to evaluate overall and event-free survival (at 2 years post-HSCT)
- to estimate the risks of serious adverse events (at 1 year post-HSCT)
- to evaluate the rate of primary engraftment and risks of graft failure (at 2 years post-HSCT)
- to estimate risks and severity of acute and chronic graft versus host disease (at 1 and 2 years post-HSCT, respectively)
- to estimate risks of viral infections (at 1 year post-HSCT)
- to evaluate transplant related mortality (at 2 years post-HSCT)
- to estimate a kinetics of immune recovery (at 2 years post-HSCT)
- to estimate levels of donor chimerism (at last follow up)

### **2.4. Primary endpoint**

1. Overall survival (OS) 2 years after HSCT, defined as time from transplantation to death of any cause

### **2.5. Secondary endpoints**

2. Cumulative incidence of transplant-related mortality 1 year after HSCT
3. Cumulative incidence and severity of acute GVHD II-IV grade 1 year after HSCT

4. Cumulative incidence of chronic GVHD 2 years after HSCT
5. Number of participants, who reached immune recovery (CD3+, CD19+ lymphocytes subsets and intravenous immunoglobulin independence) 2 years after HSCT
6. Percentage of patients with full (more than 90%) donor chimerism among survivals at last follow-up
7. Cumulative incidence of CMV reactivation 1 year after HSCT

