### ***3.4 Immune reconstitution***

For immune recovery kinetics in whole blood will be analysed monthly until day + 180 and then once every 3 months until day + 360 routinely. Patients with no demonstrated immune recovery at 1 year after HSCT will be monitored via individual protocols. Lymphocyte subsets analysis will be performed via flow cytometry. Routinely monitored cell lines include: CD3+, CD19+, CD3-CD16+CD56+, CD3+CD16+CD56+, CD3+TCRalpha/beta+, CD3+TCRgamma/delta+, CD3+CD45RA+CD197+.

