### ***3.5 Statistical analysis***

The patients will be censored at the time of death or at the last FU in survivors (the minimum FU period in survivors was 0,5 years).

The probability of overall and event free survival (OS and EFS) will be estimated by the Kaplan-Meier method. For EFS analysis as events will be considered graft failure, deaths, severe graft dysfunctions due to mixed chimerism, severe organ damage due to HSCT complications. The probabilities of acute and chronic GVHD, graft failure, viral reactivations and transplant-related mortality will be estimated with cumulative incidence curves (considering competitive risks, e.g., graft failure or death).

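### Endpoint 5 is a bare count of immune recovery at 2 years, with no denominator and no rule for death or short follow-up; a competing-risk cumulative incidence should replace it

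*Combined protocol and SAP*

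**What the plan says.** Section 2.5 lists as endpoint 5: "Number of participants, who reached immune recovery (CD3+, CD19+ lymphocytes subsets and intravenous immunoglobulin independence) 2 years after HSCT". The matching aim in section 2.3 is "to estimate a kinetics of immune recovery (at 2 years post-HSCT". Neither place names a denominator, gives CD3+ or CD19+ values, or says whether recovery is meant by 2 years or at 2 years.

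The other secondary endpoints are better specified. Endpoint 4, at the same horizon, is "Cumulative incidence of chronic GVHD 2 years after HSCT"; endpoints 2, 3 and 7 are also cumulative incidences, and endpoint 6 is a percentage among survivors.

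Section 3.5 states that "the minimum FU period in survivors was 0,5 years". It uses Kaplan-Meier for OS and EFS. GVHD, graft failure, viral reactivations and transplant-related mortality "will be estimated with cumulative incidence curves (considering competitive risks, e.g., graft failure or death". Immune recovery is on neither list.

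Section 3.4 schedules immune testing "monthly until day + 180 and then once every 3 months until day + 360 routinely". After that, "Patients with no demonstrated immune recovery at 1 year after HSCT will be monitored via individual protocols". The routine list there ("Routinely monitored cell lines include: CD3+, CD19"+ and further subsets) holds cell lines only, so immunoglobulin independence, a component of the endpoint, is not on it.

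**The concern.** A raw number at a fixed horizon is interpretable only if every patient has either been observed to that horizon or had a competing event first. The plan accepts survivors whose follow-up ends 1.5 years before the horizon. A survivor not yet recovered at that point adds nothing to the count, exactly as a patient who never recovers adds nothing. Two data cuts of the same cohort would therefore report different numbers for the same true recovery, and the result could not be compared cleanly with another series.

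The second difficulty is assessment. If the endpoint means status at 2 years, patients recovered by 1 year have no planned test near that time. If it means recovery at any time up to 2 years, recoveries after day +360 are found only as far as each patient's individual monitoring looks for them.

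The OS, EFS, transplant-related mortality, GVHD and graft-failure analyses are not affected.

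**Working it through.** **From the documents.** The plan gives no sample size, expected recovery rate or follow-up distribution for this endpoint, so there is no figure to reproduce. Two intervals follow from the text:
- Minimum follow-up to the horizon: 2 − 0.5 = 1.5 years.
- Last routine immune test to 2 years: 730 − 360 = 370 days.

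**Illustration 1: short follow-up alone.** Everything here is assumed, per 100 transplanted:
- Recovery by day +360 (0.986 years) and by 2 years: 60 and 70, 65 and 75, or 70 and 75.
- Recovery times uniform from 0.25 years to day +360, then uniform to 2 years.
- Death or graft failure first in 15.
- Follow-up uniform from 0.5 to F years, F = 3, 4 or 5. The share followed under 2 years is 1.5/(F − 0.5) = 60%, 43% or 33%.
- Recovery is seen as it occurs, so testing gaps play no part.

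A recovery at time t is counted with probability 1 if t ≤ 0.5, and otherwise (F − t)/(F − 0.5).

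- Early recoverers: the share recovering before 0.5 years is 0.25/0.736 = 0.340. The rest recover at 0.743 years on average. For F = 3 the counted share is 0.340 + 0.660 × (3 − 0.743)/2.5 = 0.936.
- Late recoverers: mean time 1.493 years. For F = 3 the counted share is (3 − 1.493)/2.5 = 0.603.
- Count for the 60/70 case: 60 × 0.936 + 10 × 0.603 = 62.2, against a true 70.

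| Recovered by day +360 / 2 years | F = 3 | F = 4 | F = 5 |
|---|---|---|---|
| 60 / 70 | 62.2 | 64.4 | 65.7 |
| 65 / 75 | 66.9 | 69.2 | 70.5 |
| 70 / 75 | 68.5 | 70.4 | 71.4 |

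The shortfall runs from 75 − 71.4 = 3.6 to 75 − 66.9 = 8.1. If no survivor had 2 years of follow-up (F = 2), it would be about 11 to 14. In simulation under the same assumptions, the competing-risk (Aalen-Johansen) estimate returns 69.9 to 70.0 and 74.9 to 75.0 for F = 3 to 5.

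**Who drops out.** Among patients free of death or graft failure and followed under 2 years, the counted share is 0.893 for early and 0.338 for late recoverers. In the 60/70 case that is (60 × 0.893 + 10 × 0.338)/85 = 67%; in the 70/75 case it is (70 × 0.893 + 5 × 0.338)/85 = 76%. Most survivors with short follow-up are therefore still counted as recovered.

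**Illustration 2: testing after day +360 alone.** With complete 2-year follow-up, suppose 25% to 50% of patients not recovered at day +360 are not tested again. The count loses the untested share times the late recoveries: 0.25 × 5 = 1.25 up to 0.50 × 10 = 5.

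**Illustration 3: the proposed estimate on actual visits.** I simulated the section 3.4 visits, with tests about every 90 days from day +360 to 2 years assumed and patients not yet recovered censored at their last assessment. The day +360 estimate is within about 0.2 points of the truth. At 2 years it is within 0.7 points if half of the non-recovered go untested at random. It is about 2 to 4 points too high if late recoverers are all tested and half of the others are not, and about 2 to 4 points too low if half of the late recoverers go untested.

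**The case against.** The strongest case on the other side has four parts.

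First, a reader might infer that all survivors with short follow-up count as not recovered. No section says so, and a patient who recovered before last follow-up has reached the endpoint on its ordinary wording. If all survivors followed under 2 years were treated as failures, the 60/70 case with F = 3 would give 0.40 × 70 = 28, not 62. Only those not yet recovered at last follow-up are lost, and even that is the default result of a raw count, not a stated rule.

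Second, a reader might infer that nobody is tested after day +360. Section 3.4 provides individual monitoring for patients without recovery at 1 year, who are the only ones in whom a first recovery can still occur. What is missing is a common schedule for them, and any planned test for those already recovered.

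Third, no bias size comes from the documents. A minimum follow-up of 0.5 years does not show how many survivors fall short of 2 years. This stands, and the figures above are illustrations only.

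Fourth, the gain at 2 years is uncertain: selective testing can move the proposed estimate by 2 to 4 points, which overlaps the lower end of the shortfall it corrects. This also stands and limits what the 2-year figure can claim. It does not rescue the count, which depends on the same tests and has the follow-up shortfall as well.

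**Conclusion.** The point holds in limited form. Endpoint 5 has no denominator, no by-or-at definition, and no handling of death or of follow-up under 2 years. Read as recovery by 2 years, the count is too low whenever some survivors not yet recovered are cut off early, and it varies with the data-cut date. The direction follows from the text; the size does not. Under the assumed recovery of 70 to 75 per 100 and follow-up uniform to 3, 4 or 5 years, the shortfall is about 4 to 8 per 100. If all survivors had 2 years of follow-up, this shortfall would be nil. Read as status at 2 years, the endpoint lacks planned data for recovered patients, and the size of that error is unknown.

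This is a descriptive secondary endpoint with no stated test, so the change is worth making because it is cheap and uses a method the plan already has, not because the main result is at risk.

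**What to change.** 1. In section 2.5, define immune recovery as first reached: the first visit at which all components are met. Set the CD3+ and CD19+ values before analysis, and record immunoglobulin independence at the same visits.
2. Replace the count with the cumulative incidence of immune recovery in all transplanted patients, and add it to the section 3.5 list. Death and graft failure are competing events for this endpoint; patients not yet recovered are censored at their last immune assessment.
3. Report it at day +360, where routine data exist, and at 2 years. Label the 2-year figure descriptive unless patients not recovered at day +360 are assessed on a common schedule to 2 years or their last follow-up. Under a first-reached definition, retesting patients who have already recovered cannot change the estimate and is not needed.

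Cost: wording changes, recovery values fixed in advance, one item added at existing visits, and slightly more analysis work. The 2-year figure may end up descriptive only, and it can be biased if testing after day +360 depends on whether the patient is recovering. A first-reached definition also does not capture later loss of recovery, which the plan should acknowledge.

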#### ***3.2 GVHD, Viral infections and Serious adverse events***

Acute and chronic GVHD will be diagnosed and graded using standard guidelines (10). For cytomegalovirus (CMV) and Epstein-Barr virus (EBV) detection in blood and other biologic liquids quantitative real-time polymerase chain reaction (PCR) analysis will be used. CMV and EBV levels will be routinely monitored weekly until CD41 T-cell recovery was above  $0.3 \times 10^9/L$ . CMV disease will be identified with the detection of CMV in affected tissue. To grade the severity of serious adverse events, the National Cancer Institute Common Terminology Criteria for Adverse Events (CTCAE) will be used.

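### CMV PCR is scheduled only until each patient's own T-cell recovery, while endpoint 7 runs to 1 year, so the reported incidence can be too low

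*Combined protocol and SAP*

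**What the plan says.** Endpoint 7 in section 2.5 is "Cumulative incidence of CMV reactivation 1 year after HSCT". The matching objective in section 2.3, "to estimate risks of viral infections (at 1 year post-HSCT"), has the same horizon.

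Section 3.2 states that for CMV and EBV detection "quantitative real-time polymerase chain reaction (PCR) analysis will be used". It gives the only viral testing schedule: "CMV and EBV levels will be routinely monitored weekly until CD41 T-cell recovery was above" 0.3 x 10^9/L. The marker reads CD41, which may be a misprint or a text-reading fault for CD4+. The schedule has no calendar end. No section schedules viral PCR after the trigger or says what happens if the count falls again.

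Section 3.4 says that immune recovery in blood is "analysed monthly until day + 180 and then once every 3 months until day + 360 routinely", and section 3.3 uses the same timetable for chimerism. Neither attaches viral PCR to those visits.

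Section 3.5 says that the probabilities of several outcomes, viral reactivations among them, "will be estimated with cumulative incidence curves (considering competitive risks, e.g., graft failure or death"). Its one censoring rule is "The patients will be censored at the time of death or at the last FU in survivors", and it adds that "the minimum FU period in survivors was 0,5 years". The end of PCR surveillance is not mentioned.

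**The concern.** The endpoint has a fixed horizon, but scheduled measurement of it ends on a date that differs between patients and is set by their immune recovery. Reactivation is found by PCR, so an untested asymptomatic episode cannot be counted. After the trigger, whether a reactivation enters the data depends on unscheduled testing. If the analysis follows the general censoring rule, a patient released from weekly PCR in month 3 is carried as CMV-free to 1 year, or to last follow-up if that is sooner, with no planned test behind that status.

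Two things are at stake. The figure would be reported as a 1-year incidence although it covers a shorter, patient-dependent window. Also, section 1 presents better immune reconstitution as a possible benefit of the technique and links slow reconstitution after other depletion methods to infections. A descriptive remark that faster recovery goes with less CMV would partly reflect shorter testing in patients who recover faster.

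**Working it through.** The documents state no CMV incidence, time to recovery or sample size, so there is no figure to reproduce. The check has two parts: the text set side by side, then an illustration on assumed inputs.

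**1. The windows compared**

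| Element | Where | Ends at |
|---|---|---|
| Endpoint 7 and viral objective | 2.5, 2.3 | 1 year |
| Scheduled CMV PCR | 3.2 | patient's T-cell recovery above 0.3 x 10^9/L |
| Chimerism and immune sampling | 3.3, 3.4 | day +360, no viral PCR attached |
| Censoring | 3.5 | death or last follow-up |

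The second row can end well before the first, and the fourth does not take account of it. As an assumption, suppose the trigger is met between day +120 and day +240. Scheduled PCR then covers 120/365 = 33% to 240/365 = 66% of the year, leaving 365 - 240 = 125 to 365 - 120 = 245 days without scheduled PCR.

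**2. Direction, for a single patient**

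Let p be the 1-year CMV risk without recovery, H = -ln(1 - p) the constant yearly hazard, t the recovery time in years, and r the ratio of the hazard after recovery to that before. If nothing is detected after the stop:

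- true risk = 1 - exp(-H[t + r(1 - t)])
- observed risk = 1 - exp(-Ht)

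Observed can never exceed true. With p = 0.5 (so exp(-H) = 1/2) and r = 0.25, both assumed:

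- t = 0.25: observed 1 - 2^(-0.25) = 15.9%, true 1 - 2^(-0.4375) = 26.2%, a loss of about 10 points
- t = 0.50: observed 1 - 2^(-0.5) = 29.3%, true 1 - 2^(-0.625) = 35.2%, a loss of about 6 points
- t = 0.75: observed 1 - 2^(-0.75) = 40.5%, true 1 - 2^(-0.8125) = 43.1%, a loss of about 3 points

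**3. Averaged over patients**

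The simulation used 400,000 patients per scenario. Every input is an assumption: lognormal recovery time (median 3, 6 or 9 months, log-SD 0.5); p of 30% or 50%; r of 0.1, 0.25, 0.5 or 1; hazard either constant or concentrated early (decay rate 6 per year). Death and graft failure were left out, and no reactivation after the stop was detected. Any unscheduled testing would make the losses smaller.

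Share of true 1-year first reactivations not observed:

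| Median recovery | Constant hazard | Early-concentrated hazard |
|---|---|---|
| 3 months | 19-68% | 2-21% |
| 6 months | 7-42% | 1-7% |
| 9 months | 3-24% | 0-3% |

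Example (constant hazard, p = 50%, median 6 months, r = 0.25): true 36.1%, observed 30.5%, a loss of 5.6 points. In the earlier-recovering half, 29.8% falls to 21.4% (8.4 points). In the later-recovering half, 42.4% falls to 39.6% (2.8 points). The earlier half lost more in every scenario; within a scenario all patients had the same hazard before recovery and the same r.

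**4. Censoring at the last PCR**

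If patients leave the risk set at recovery, the curve estimates the risk as if nobody recovered, which is p. In the same example that is 50.0% against a true 36.1%, an error of 50.0 - 36.1 = 13.9 points upwards, compared with 5.6 downwards for leaving patients in. Only at r = 1 does this censoring give the true value, and r is exactly what would go unobserved.

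**The case against.** The strongest reply is that section 3.2 ends routine weekly monitoring and does not forbid later PCR. A reader might infer that testing stops altogether and that late reactivations are certain to be missed; the text does not say so. What stands is that later testing is unscheduled, so ascertainment after the trigger is neither planned nor equal across patients.

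Section 3.5 gives one general censoring rule and no risk-set rule specific to CMV. Counting unsampled time as event-free is therefore what follows from applying the plan as written, not something it states. Survivors with less than 1 year of follow-up are censored sooner.

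A reader might also equate the trigger with endpoint 5. They are related but different: endpoint 5 combines CD3+ and CD19+ recovery with immunoglobulin independence at 2 years. Nor does the plan include an analysis of CMV against immune recovery, so circularity is a caution for interpretation, not a flaw in a planned comparison.

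Finally, the endpoint is secondary and descriptive and does not touch the primary endpoint, overall survival. A patient who reactivated before release is already counted, so only first reactivations after release are at issue. If risk is mostly early, they may be few. All of this limits the size and weight of the point, but none of it closes the gap between schedule and horizon.

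**Conclusion.** The point holds as a mismatch between a 1-year endpoint and a testing schedule that ends at each patient's T-cell recovery. First reactivations after the stop are not systematically ascertained. From this source the 1-year cumulative incidence can only be too low, and more so in patients who recover early because they go unsampled for longer, assuming that their risk after recovery is not much lower than that of others.

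A reader might want a definite percentage-point bias. The documents do not support one. The 5.6 points in the example and the 0-68% span across scenarios rest entirely on assumed recovery times, CMV risks and hazard ratios, with no detection after the stop. The loss may be negligible if CMV risk is concentrated early. Confidence is high in the mismatch and its direction, and low in its size.

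One related gap makes the stop date hard to reproduce. If the marker in section 3.2 is CD4+, it is not among the routinely monitored cell lines in section 3.4, and the two passages should be reconciled.

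**What to change.** Leave the weekly monitoring rule for care unchanged. Add to section 3.2 that, for endpoint ascertainment, CMV PCR is run in every patient after weekly monitoring ends, on the samples already taken for chimerism and immune monitoring (each month to day +180, then quarterly to day +360). Include EBV PCR to serve the viral infection objective. Report the time each patient spent under weekly and under sparse surveillance.

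The cost is a few PCR tests per patient, with no new visit. A patient released at day +120 would have four further time points (days +150, +180, +270, +360), and one released at day +240 would have two (days +270, +360). There are downsides. Sparse late sampling dates events less exactly and can still miss brief viraemia, so the bias is reduced but not removed. The reported incidence may rise slightly. The added results will also reach treating clinicians, so the plan should say how they are handled.

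If the added PCR is not done, relabel endpoint 7 as reactivation detected during routine surveillance and report the surveillance time beside it. Do not censor at the last PCR: stopping depends on immune recovery, so that censoring is informative and can do more harm than leaving patients in the risk set.
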